## 6.8. Termination Date (= censoring date for the final ITT analyses)

### CIP chapter 8.9.5 Point of enrollment and study termination

...

*Regular point of termination for the individual patient is the respective date of the final study termination visit.*

*For all non-regular study terminations, the following rules apply:*

- *In case of patient death, the date of study termination is the date of death.*
- *In case of HTX, the discharge date from the HTX procedure's hospitalization is the date of study termination.*
- *In case of withdrawal of consent, the date of study termination is the date of withdrawal of consent.*
- *If patient is lost to follow-up, the date of termination is the date of last contact of the investigator or of the CRO that collects AEs. Data from the HMSC will not be used to ascertain the vital status of patients for any primary analysis because this might introduce a bias in favor of the BM arm.*
- *If patient is defined as drop-out patient for any other reason, the date of study termination is the date on which the reason for the drop-out became effective, i.e. the date on which a violation of inclusion criteria was discovered, or on which the investigator excluded the patient for safety reasons.*

The variable term\_date compromises the above definition, which is an instruction for the investigator how to report the termination date. The variable term\_date will be checked during monitoring and during the blind review of the data before CDMS freeze or closure.

All remaining patients are terminated when the formal study termination is announced. Therefore, no individual study termination can be later than the formal study termination.

Data file: Identifier	Variable name	Variable label	Variable level	Nominal values
patient_display_id_full				
study_termination	term_date	Date of study termination	date	n.a.
study_termination	regular_yn	regular study termination	nominal	Yes / No

## 7. Analysis Sets

### 7.1. ITT Analysis Set

*CIP chapter 11.1.2 Full Analysis set based on the ITT principle*

*The analysis of the primary hypothesis is performed on the full analysis set based on the intention-to treat (ITT) principle; i.e. the set of data from all randomized patients by minimal and justified elimination of subjects. This set is used to estimate the effect of the experimental intervention with greatest external validity. Subjects allocated to randomization group are analysed as members of that group irrespective of their compliance to the planned course of treatment, e.g. cross-over to the other group.*

*The ICH-E9 guideline states that "there are a limited number of circumstances that might lead to excluding randomized subjects from the full analysis set including ... the failure to take at least one dose of trial medication and the lack of any data post randomization."*

*In accordance to this guideline, the following patients will be excluded from the analysis set*

- *Patients of the BioMonitor group and control group in case of a drop-out before discharge from the index hospitalization*
- *Patients without signed informed consent form*

Data file: Identifier	Variable name	Variable label	Variable level	Nominal values
patient_display_id_full	ic_yn	Patient has provided written informed consent	nominal	Yes / No
enrollment	term_date	Date of study termination	date	n.a.
study_terminatuion	date_effrand_ITT_SAR	Date effective randomization for ITT analysis (discharge from index hospitalization)	date	n.a.
data_SAR	analysis_set_itt_SAR 	ITT analysis set	nominal	Yes / No

## 7.2. PP Analysis Set

### CIP. Chapter 11.1.3 Per-protocol Analysis Set

A supportive analysis of the primary hypothesis is performed on the per-protocol set (efficacy sample), which is a subset of the patients from the above full analysis set who complied sufficiently with the protocol. This set is used to ensure that the data would be likely to exhibit the effects of treatment according to the underlying scientific model.

The Per-Protocol Analysis Set is the subgroup of the Full Analysis set after exclusion of

- Patients with violation of in- or exclusion criteria at enrollment
- Patients with major deviations from the CIP in accordance with the definition given in section 14.1
- Patients of the BioMonitor group without implanted device or drop-out less than 1 month after implantation
- Patients of the control group in case of a drop-out less than 1 month after index hospitalization

### CIP chapter. 14.1 CIP compliance and exceptions

... A deviation is any failure to follow, intentionally or unintentionally, the requirements of the CIP, including laws, guidelines and other regulation as far as required by the CIP, as well as applicable amendments. Deviations that are likely to seriously affect or that actually have seriously affected the rights or safety or wellbeing of subjects or the scientific integrity of the clinical investigation are major deviations (in the U.S. the term "violation" will be used). Otherwise they are minor deviations (in the U.S. simply referred to as "deviations").

Erroneous, spurious or missing data in a CRF is not a deviation in itself and is handled according to the query processes described in the data management section of this CIP. However, the underlying reason might be a deviation.

Intentional, anticipated deviations from the CIP are only allowed if the deviation is required to protect the subject's rights, safety and well-being or the scientific integrity of the study. In such a case, the investigator will contact the sponsor and obtain prior approval for the deviation. If the deviation occurs in an emergency situation or any other unforeseen situation and is required to protect the patient's life or wellbeing, no prior sponsor approval is required. In case of a study deviation, either anticipated or unanticipated, both the investigator as well as the sponsor may request drop-out/premature study termination of the patient, based on the nature and/or consequences of the deviation.

To be more precise, the per-protocol analysis set is given by the ITT analysis set excluding

- patients with violation of in- or exclusion criteria,
- patients with study termination before the effective randomization date for the PP analyses
- patients randomized to the BioMonitor group without implantation
- patients randomized to the the control group with implantation before the effective randomization date for the PP analyses, and
- patients with other major protocol violations before the effective randomization date. Major protocol deviations are documented in the CDMS file deviation\_form\_site. None of the events reported here were found to be relevant here except violation of in- an exclusion criteria and cross-overs contrary to randomization. However, these cases will identified by other procedures defined here and this CRF doesn't have to be considered.

 Note: Patients with major protocol violations later than 30 days after index discharge are included in the per-protocol analysis set. However, data after the occurrence of the protocol violation is not taken into account (see chapter 6.5).

Data file: Identifier	Variable name	Variable label	Variable level	Nominal values
patient_display_id_full				
enrollment	in01_yn, in02_yn, in03_yn, in04_yn	Inclusion criteria	nominal	Yes /No
enrollment	ex01_yn, ex02_yn, ex03_yn, ex04_yn, ex05_yn, ex06_yn, ex07_yn, ex08_yn, ex09_yn, ex10_yn	Exclusion criteria	nominal	
data_SAR	analysis_set_pp_SAR 	Per-protocol analysis set	nominal	Yes / No

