#### 11.1.3 Per-Protocol Analysis Set

A supportive analysis of the primary hypothesis is performed on the per-protocol set (efficacy sample), which is a subset of the patients from the above full analysis set who complied sufficiently with the protocol. This set is used to ensure that the data would be likely to exhibit the effects of treatment according to the underlying scientific model.

The Per-Protocol Analysis Set is the subgroup of the Full Analysis set after exclusion of

- Patients with violation of in- or exclusion criteria at enrollment
- Patients with major deviations from the CIP in accordance with the definition given in section 14.1
- Patients of the BioMonitor group without implanted device or drop-out less than 1 month after implantation
- Patients of the control group in case of a drop-out less than 1 month after index hospitalization

Time-to-first-event data are censored after occurrence of

- Cross-overs from the BioMonitor group to the control group or vice versa
- Major protocol violations as defined in section 14.1

Primary endpoints are not taken into account in the BioMonitor group and in the control group until 1 month after discharge from the index hospitalization.

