### 11.8 Procedures for reporting of deviations to the statistical plan

Deviation(s) from the statistical plan described here are reported via amendments to the CIP and / or via a separate SAP.

An SAP version 1.0 was written as a separate document before 1st patient-in including a more technical and detailed elaboration of the statistical considerations as described here.

The SAP is reviewed and possibly updated based on a blind review of the data before breaking the blind for the interim analysis or the final analysis.

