## 14 DEVIATIONS FROM CLINICAL INVESTIGATION PLAN

### 14.1 CIP compliance and exceptions

All sponsor personnel, all investigational site personnel as well as other third parties, who are involved in tasks covered by this CIP, are generally obliged to comply with this CIP. A U.S.-specific amendment is available for investigational sites in the U.S. to better address U.S. regulation. The U.S.-specific CIP amendment is valid for U.S. sites, even if differing from this CIP.

A deviation is any failure to follow, intentionally or unintentionally, the requirements of the CIP, including laws, guidelines and other regulation as far as required by the CIP, as well as applicable amendments. Deviations that are likely to seriously affect or that actually have seriously affected the rights or safety or wellbeing of subjects or the scientific integrity of the clinical investigation are major deviations (in the U.S. the term "violation" will be used). Otherwise they are minor deviations (in the U.S. simply referred to as "deviations").

Erroneous, spurious or missing data in a CRF is not a deviation in itself and is handled according to the query processes described in the data management section of this CIP. However, the underlying reason might be a deviation.

Intentional, anticipated deviations from the CIP are only allowed if the deviation is required to protect the subject's rights, safety and well-being or the scientific integrity of the study. In such a case, the investigator will contact the sponsor and obtain prior approval for the deviation. If the deviation occurs in an emergency situation or any other unforeseen situation and is required to protect the patient's life or wellbeing, no prior sponsor approval is required. In case of a study deviation, either anticipated or unanticipated, both the investigator as well as the sponsor may request drop-out/premature study termination of the patient, based on the nature and/or consequences of the deviation.

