### 1.4. Unblinding

In the context of the first interim analysis in March 2020, the DSMB discovered inconsistencies in adverse event reporting and consequently recommended unblinding of limited sponsor personnel to perform further investigations on the matter.

For this reason, all persons responsible for SAP 3.0 were unblinded.

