### CIP chapter 14.1 CIP compliance and exceptions

... A deviation is any failure to follow, intentionally or unintentionally, the requirements of the CIP, including laws, guidelines and other regulation as far as required by the CIP, as well as applicable amendments. Deviations that are likely to seriously affect or that actually have seriously affected the rights or safety or wellbeing of subjects or the scientific integrity of the clinical investigation are major deviations (in the U.S. the term "violation" will be used). Otherwise they are minor deviations (in the U.S. simply referred to as "deviations").

The first major protocol violation will be used for censoring for the per-protocol analysis when there is no previous primary endpoint:

- Date of initial implantation in patients randomized to the control group.
- Date of "elective replacement indicator" (ERI) reported on an Arrhythmia Notification CRF, in patients randomized to the BioMonitor group if they do not receive a new device.
- First date of other major protocol violations after the effective randomization date. Major protocol deviations are documented in the CDMS file deviation\_form\_site. None of the events reported here were found to be relevant here except violation of in- an exclusion criteria and cross-overs contrary to randomization. However, these cases will be identified by other procedures defined here and this CRF doesn't have to be considered.

---

 Note: A patient with implantation before effective randomization PP is not included in the PP analysis set. Thus, the initial implantation date defined here is implicitly defined as implantation after effective randomization PP.

Data file: Identifier	Variable name	Variable label	Variable level	Nominal values
record_id				
eri_form	expl_date	Date of explantation	Date	Yes / No
arrythmia_notification	reason_multi	Reason for assessment	nominal	Arrhythmia/Event notification ERI notification ...
arrythmia_notification	helpvar_dateFormCreated		date	n.a.

Data file: Identifier	Variable name	Variable label	Variable level	Nominal values
patient_display_id_full				
study_termination	term_date	Date of study termination	date	n.a.
data_SAR	date_final_PP_SAR 	Date of first major protocol violation after the effective randomization date of the PP analysis or termination date (censoring date for PP analysis when there is no previous primary endpoint)	date	n.a.

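### SAP 3.0 leaves the protocol's separate major-deviation rule for the per-protocol set without effect, on a relevance decision with no stated criterion, adopted by staff who were all unblinded

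*SAP*

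**What the plan says.** CIP 11.1.3 gives the purpose of the PP set: "This set is used to ensure that the data would be likely to exhibit the effects of treatment according to the underlying scientific model". One of its four exclusion reasons is "Patients with major deviations from the CIP in accordance with the definition given in section 14.1", listed apart from eligibility violations, a missing implant and early drop-out. One of its two censoring reasons is "Major protocol violations as defined in section 14.1", listed apart from cross-over. CIP 14.1 defines the class broadly: "Deviations that are likely to seriously affect or that actually have seriously affected the rights or safety or wellbeing of subjects or the scientific integrity".

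SAP 7.2 (exclusion) and SAP 6.7 (censoring) each keep a bullet for other major violations and name the file deviation_form_site as the place where they are recorded. SAP 7.2 then states: "None of the events reported here were found to be relevant here except violation of in- an exclusion criteria and cross-overs contrary to randomization". SAP 6.7 contains the same finding and continues: "However, these cases will be identified by other procedures defined here and this CRF doesn't have to be considered". SAP 7.2 closes in nearly the same words.

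The change history lists a further specification of major deviations for the PP analysis under version 3.0. SAP 1.4 explains that limited sponsor personnel were unblinded on the DSMB's recommendation, to look into inconsistent adverse event reporting, and adds: "For this reason, all persons responsible for SAP 3.0 were unblinded". CIP 11.8 says: "The SAP is reviewed and possibly updated based on a blind review of the data before breaking the blind for the interim analysis or the" (the sentence closes by naming the end-of-study analysis).

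**The concern.** A PP set is open to selective construction, because someone decides which departures from protocol count. The usual protection is to fix the rule in advance, or to make the decisions blind to allocation and outcome. CIP 11.1.3 supplied a rule and CIP 11.8 supplied a blind review. Here the rule was made inactive in a SAP version whose responsible persons no longer had the blind, and the wording (events *were found* not relevant) indicates that the records had already been examined.

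At stake is how the PP result can be read. SAP 11.6 repeats the test of the primary hypothesis in this set. If patients with a deviation classed as major remain in it and are followed past that deviation, a reader cannot tell whether agreement or disagreement between the PP and intention-to-treat results reflects the intervention or the choice of what to set aside.

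**Working it through.** No arithmetic applies: the documents give no number of major deviations, overall or by arm. The check is to set the CIP rules beside their SAP counterparts.

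| CIP 11.1.3 | SAP 3.0 | Still operates? |
|---|---|---|
| Exclude: eligibility violation | 7.2, from the enrollment-form criteria | Yes |
| Exclude: BioMonitor patient without implant, or early drop-out | 7.2, no implantation; termination before PP start (discharge + 30 days) | Yes |
| Exclude: control patient, early drop-out | 7.2, same termination rule | Yes |
| Exclude: major deviation | 7.2, bullet kept, form not considered | No |
| Censor: cross-over | 6.7, date of implantation in controls | Yes |
| Censor: major violation | 6.7, bullet kept, form not considered | No |

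The SAP also excludes controls implanted before the PP start and censors BioMonitor patients at the elective replacement indicator if no new device is given.

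1. *What is lost.* One of four exclusion reasons and one of two censoring reasons have no effect. Both are the residual major-deviation category. Everything else runs on dated or recorded facts.

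2. *Could other rules catch the same cases?* For eligibility and cross-over, yes, as the SAP says. For the rest, no. CIP 8.1 sets an implantation limit of 8 weeks from enrollment, and CIP 9.3 makes arrhythmia-detection programming and Home Monitoring activation mandatory. None of these has a PP rule of its own. The documents do not say that any such breach occurred or was classed as major. The point is that one would pass unexamined.

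3. *Later entries.* The instruction to disregard the form carries no date. SAP 5.9 places the analyses after database closure, so a major deviation entered between SAP 3.0 and closure is disregarded as well.

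4. *Was it declared as a departure?* CIP 11.8 allows departures from the statistical plan to be reported in the SAP. SAP 7.2 instead presents its rules as a more precise statement of the CIP. By contrast, SAP 5.6 says openly that the atrial-fibrillation-history subgroup is dropped, and why. For the PP change there is no relevance criterion, list or count by arm.

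5. *Completeness of the source.* CIP Appendix A says non-U.S. sites record noncompliance on a paper log and U.S. sites on an electronic form, while CIP 8.4.1 lists a deviation form among the CRFs. CIP 14.2.1 has the sponsor merge site logs into one study deviation log. The SAP names only deviation_form_site, so it is unclear whether all major deviations were in view.

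6. *Reach.* The category touches one repeat of the primary test and two of the five hazard-ratio conditions in SAP 11.6. All five hazard ratios are calculated only if the primary alternative hypothesis is accepted. CIP 11.5 ties pass or fail to the full analysis set.

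**The case against.** The strongest reply is that a relevance decision is reasonable in itself. The 14.1 definition covers deviations that affect only rights or safety and may have no bearing on efficacy. Removing those patients would not serve the stated purpose of the set. This stands, and it is why applying the CIP rule mechanically should not become the main PP analysis. The BioMonitor arm also carries more protocol obligations (implantation timing, programming, Home Monitoring), so mechanical exclusion could fall unequally on the arms. What the reply does not supply is the criterion used, or a list that would let a reader judge it.

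A second reply is that the unblinding is already disclosed in SAP 1.4 and the change is listed under version 3.0. That is so, but the two are not connected, and the change is not described as a departure from CIP 11.1.3.

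A third is that the study is open, so blinding means little here. Yet CIP 11.8 still bases SAP updates on a blind review, and SAP 6.8 still relies on one for termination dates.

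Two stronger readings are tempting. A reader might infer that the whole PP set rests on an unblinded judgement. It does not: most of its rules are objective and only the residual category is inactive. A reader might also infer that deviations were set aside by people who knew outcomes by arm. The documents do not say who reviewed the deviations, when, or what they had seen. They establish only that those responsible for the version that adopted the result were unblinded.

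**Conclusion.** The point holds in a limited form. SAP 3.0 makes the CIP's residual major-deviation category inoperative for both PP exclusion and PP censoring. The text entered in a version whose responsible persons were all unblinded, and it gives no criterion or by-arm list. Neither the size nor the direction of any effect on the PP result can be worked out from the documents. Keeping imperfectly treated patients would usually draw the PP result towards the intention-to-treat result, but nothing here shows that this happened.

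The primary test, its significance level and the primary conclusion are untouched, and it would be wrong to read this as a threat to them. The conclusion assumes that the past-tense finding reflects a look at actual records, and that the change-history entry under version 3.0 refers to this text. The point should be corrected because it concerns a planned repeat of the primary test and costs little to settle.

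**What to change.** Keep the SAP 3.0 PP set as the main PP analysis. Then:

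- Add to SAP 6.7, 7.2 and 11.6 a PP sensitivity analysis that applies CIP 11.1.3 as written. Every deviation classed as major in the consolidated study deviation log (all sites, including U.S. violations, up to database closure) excludes the patient if dated before the PP start and censors at its date if later.
- Tabulate all major deviations by type and arm, marking those that the SAP 3.0 set disregards.
- State in SAP 7.2 that the relevance decision departs from CIP 11.1.3 and was adopted by unblinded staff.

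The cost is SAP wording, merging the deviation log and one more PP run. That run will have a smaller set and possibly unequal exclusions between arms, which is why it belongs as a sensitivity analysis. If the two PP results agree, the question is closed. If they differ, the table shows which deviations to examine.

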### 14.2 Recording, reporting and analysing deviations

#### 14.2.1 Site specific deviations

Investigational sites inform the sponsor immediately about any deviation as they become aware of it. In addition, compliance to the CIP is verified by the sponsor through monitoring visits. Each site-specific deviation is recorded by monitors in the respective site deviation log and assessed for the need of corrective or preventive actions. Additional information on the type of deviation, actions taken and outcome should be recorded in the monitoring visit reports. The deviations will be discussed with the PI or authorized designee. A re-training to the respective CIP specification will be performed to prevent further deviations. The retraining will be documented accordingly. Other additional suitable actions may be initiated after consultation of the clinical project management. All information from site deviation logs is consolidated by the sponsor in one overall study deviation log.

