Noncompliance with study protocol	
Noncompliance classification: Major Deviation: Deviation that are likely to seriously affect or that actually have seriously affected the rights or safety of wellbeing of subjects or the scientific integrity of the clinical investigation. Minor deviation: Other deviation from the protocol that do not meet the definition for Major Deviation.
 
All protocol noncompliances are recorded by each site on a paper deviation log
	
Noncompliance classification: Protocol Violation: Major deviation where the protocol requirements and/or regulatory guidelines are not followed, and are generally more serious in nature. They are considered to potentially affect the scientific soundness of the study and/or rights, safety or welfare of subjects. Protocol Deviation: Other deviation from protocol that does not meet the definition of violation and are generally less serious in nature and may not require IRB notification as long as they do not affect the rights, safety, or welfare of the study subject.
 
All protocol noncompliances are recorded on a Protocol Non-compliance eCRF within the EDC system.
	
Noncompliance classifications in the regions are similar in definition, but each protocol follows the applicable regulatory requirements. The statements vary in sentence structure and word choice.
 
The U.S. records noncompliances electronically as part of their standard processes. All noncompliances from both regions will be merged for reporting purposes.

Title	BIOGUARD MI, version 7.0	BIOGUARD MI, U.S. version June 12, 2019 amended April 06, 2021	Justification
SAE/S(U)ADE/DD	Per ISO14155 The investigator reports: 
 
Adverse events
 
Serious adverse events
 
Serious adverse device effect
 
Unanticipated serious adverse device effect
 
Device deficiency
 
	Per ISO 14155 and FDA 21 CFR Part 812 The investigator reports: 
 
Adverse events
 
Serious adverse events
 
Unanticipated adverse device effects
 
Serious adverse device effect
 
Unanticipated serious adverse device effect
 
Device deficiency
 
Device complaint
 
	To ensure proper reporting, all sites will follow ISO14155 and U.S. sites will follow FDA 21 CFR Part 812, in addition to ISO 14155

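### SAP 7.2 lists only the enrollment yes/no items for eligibility violations and waives the deviation form, so some violations found after discharge can stay in the per-protocol set

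*SAP*

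**What the plan says.** CIP 11.1.3 defines the PP set as the full analysis set less several groups, the first being "Patients with violation of in- or exclusion criteria at enrollment". The SAP 7.2 bullet list carries this over as "patients with violation of in- or exclusion criteria". Neither wording limits when or how the violation comes to light.

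The SAP 7.2 variable table takes the eligibility data from the enrollment file: the inclusion items "in01_yn, in02_yn, in03_yn, in04_yn" and the exclusion items "ex01_yn, ex02_yn, ex03_yn, ex04_yn, ex05_yn, ex06_yn, ex07_yn, ex08_yn, ex09_yn, ex10_yn".

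On the deviation file `deviation_form_site`, SAP 7.2 reports: "None of the events reported here were found to be relevant here except violation of in- an exclusion criteria and cross-overs contrary to randomization". It then concludes that "these cases will identified by other procedures defined here and this CRF" can be left out of account. SAP 6.7 repeats this waiver for PP censoring.

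CIP 14.2.1 describes where deviations end up: "All information from site deviation logs is consolidated by the sponsor in one overall study deviation log". SAP 7.2 does not refer to that log.

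**The concern.** Eligibility is checked before enrollment (CIP 9.2), so a patient enrolled in error may well carry entries that say the criteria were met. Such errors tend to surface later, at monitoring, and CIP 14.2.1 sends deviations found there to the deviation log. SAP 7.2 acknowledges that the deviation form holds eligibility violations and then sets it aside. It relies on other procedures, but the only ones visible that bear directly on eligibility are the enrollment items. Nothing in SAP 7.2 requires the two sources to agree.

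What is at stake is PP membership. CIP 11.1.3 uses this set to show the effect in patients who complied sufficiently with the protocol. If a patient whom the sponsor's own records show to be ineligible remains in it, the supportive analysis does not describe its stated population.

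**Working it through.** The plan gives no figure to reproduce. The check is to trace each rule that could remove a patient who violated a criterion at enrollment, by when the violation is found.

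1. **Found before index discharge.** CIP 8.9.4.5 treats this as premature termination. CIP 11.1.2 and SAP 7.1 remove drop-outs before discharge from the full analysis set, and the PP set is a subset of that. Result: excluded.

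2. **Found after discharge, patient terminated before discharge + 30 days.** For a patient dropped because of the violation, CIP 8.9.5 dates termination at discovery. SAP 7.2 excludes terminations before the PP effective randomization date, which SAP 6.5 sets at discharge + 30 days. Result: excluded.

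3. **Found at any time, enrollment item corrected.** CIP 12.3 has monitors check the eCRF against source and resolves discrepancies by query. SAP 5.5 expects forms to be locked for the final analysis. A corrected item would then flag the patient. Result: excluded.

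4. **Found after discharge, enrollment item not corrected, and no termination before discharge + 30 days.** The remaining sources are:
   - the deviation form, which SAP 7.2 waives;
   - the consolidated study deviation log, which SAP 7.2 does not mention;
   - the termination reason for early discovery of an eligibility violation, which SAP 8.2 uses only for description and case listings and which is not among the PP variables in SAP 7.2.

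   Result: no visible rule excludes the patient.

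Censoring does not catch case 4 either. SAP 6.7 censors PP follow-up at implantation in a control patient, at a battery replacement indication without a new device, or at termination, and it waives the deviation form a second time. A patient in case 4 who stays in the study is neither excluded nor censored for ineligibility. CIP 8.9.4.5 prescribes termination only for discovery before discharge, so remaining in follow-up after a later discovery is consistent with the protocol.

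The documents give neither the number of eligibility violations on the deviation form nor the number of enrollment items that disagree with it. The size of case 4 cannot be computed.

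**The case against.** The strongest defence is that SAP 7.2 reports the result of a review of the deviation form and calls it redundant. On this view, monitoring and queries will have corrected the enrollment items before lock, and CIP 12.3 requires open queries to be cleared before a site is closed. CIP 14.1 also sends erroneous CRF data to the query process. Much of this stands: routes 1 to 3 remove many violators, and the documents show no case in which the redundancy fails. It does not close the gap. The plan nowhere requires that every eligibility violation on the deviation form lead to a changed enrollment item, and the review is reported as past, with no rule to repeat it before lock.

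The derivation footnote for `analysis_set_pp_SAR` is not in the text available for review. The statement about sources is therefore limited to the listed variables. The waiver itself stands in the body text.

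A reader might infer more than the documents support:

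- **That every violation found after enrollment stays in the PP set.** Routes 1 to 3 show otherwise.
- **That the CDMS deviation file is incomplete for sites outside the U.S.** Appendix A says of those sites: "All protocol noncompliances are recorded by each site on a paper deviation log". But it also says that noncompliances from both regions are merged for reporting, CIP 8.4.1 lists a deviation CRF, and SAP 7.2 says major deviations are documented in the CDMS. Incompleteness is not shown.
- **That a reported count of eligibility violations will be too low.** SAP 7.2 and 8 specify no such count.
- **That the derived values in SAP 9.2 should be used to re-check eligibility.** `lvef_SAR` only selects one of two entered LVEF fields, from before or after an amendment. The SAP has ten exclusion items where CIP 8.9.3 has nine criteria, which suggests that criteria changed during the study. Applying current cut-offs to everyone could remove patients who were eligible when enrolled.

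**Conclusion.** The concern holds in a limited form. SAP 7.2 sets aside a source that it says contains eligibility violations and lists only the enrollment items in its place. A violation found after index discharge then stays in the PP set, contrary to CIP 11.1.3, unless the item is corrected or the patient terminates before discharge + 30 days.

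This is a stated rule, not merely missing detail, and it should be changed. The consequence is confined to PP membership and the supportive PP analysis. Under CIP 11.5 pass or fail rests on the full analysis set, so the primary test is untouched. The number of patients and the effect on the PP hazard ratio are unknown.

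The conclusion assumes that the missing footnote does not bring in the deviation form, which would contradict the visible text, and that at least one post-discharge violation was not carried back to the enrollment item.

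**What to change.** In SAP 7.2, and in the matching text of SAP 6.7, delete the statement that the deviation CRF need not be considered. Exclude from the PP set any patient with an eligibility violation, under the criteria in force at that patient's enrollment, recorded in any of:

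- the enrollment items in01 to in04 and ex01 to ex10;
- `deviation_form_site` or the consolidated study deviation log of CIP 14.2.1;
- the termination reason for early discovery of an eligibility violation.

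Reconcile these sources before database lock and document the result. Staff should code the violations without seeing treatment group, because SAP 1.4 says that everyone responsible for SAP 3.0 was unblinded and the SAP change history shows that version 3.0 further specified major deviations for the PP analysis. This is a safeguard, not an allegation of bias.

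The cost is a few sentences in the SAP and a merge of existing records. The small downside is that the PP set may lose a few patients.
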